9.1.17.1 Total and Differential Cell Counts in Induced Sputum

The following total and differential cell counts in induced sputum samples will be performed at the Sputum Laboratory:

- Total and differential cell counts in induced sputum (absolute [cells/mL] and percentage [%]):
 - 1) Neutrophils
 - 2) Macrophages
 - 3) Eosinophils

4) Lymphocytes

9.1.17.2 Measurement of Variables Describing Concentration of Inflammatory Biomarkers in Sputum Specimens

Sputum collection for measurement of inflammatory biomarkers will be performed at visits V1 (-2 weeks), V4 and V5 (subsequent to six and 14 weeks of double-blind treatment respectively). Sputum supernatant samples will be handled and stored according to the instructions provided in the Sputum Laboratory Manual (see [Appendix H](#)). All laboratory samples have to be clearly and fully labelled according to the Central Laboratory Manual.

Sputum samples will be analysed by the Biomarker Laboratory using the 46-biomarker Multi-Analyte Profiling (MAP) technology (Human InflammationMAP[®] v.1, Rules-Based Medicine, Inc., Austin, TX, U.S.A.).

The parameters Alpha-2 Macroglobulin, Interleukin-8 (IL-8), Monocyte Chemotactic Protein-1 (MCP-1), Matrix Metalloproteinase Type 9 (MMP-9), Tissue Inhibitor of Metalloproteinase (TIMP) and Vascular Endothelial Growth Factor (VEGF) were described in the literature as disease specific sputum marker for COPD patients [15, 24]. Within this trial a potential pharmacological effect of Roflumilast on these biomarkers of primary interest will be evaluated.

The Multi-Analyte Profiling (MAP) technology (Human InflammationMAP[®] v.1, Rules-Based Medicine, Inc., Austin, TX, U.S.A.) profile contains quantitative, multiplexed immunoassays of the above mentioned biomarkers of primary interest and in addition 40 further biomarkers attributed to an inflammatory process, summing up to 46 biomarkers overall. All biomarkers of the profile will be analysed in the same pre-specified manner with focus on the above stated biomarkers of primary interest and the remainder of the biomarkers for explorative reasons.

The **Multi-Analyte Profile (MAP)** Human InflammationMAP[®] v.1 provides the following biomarkers (*biomarkers of primary interest italicized*):

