9.1.18 Inflammatory Biomarkers in Blood Serum

9.1.18.1 Blood Withdrawal and Sample Handling Methods

Blood serum collection for measurement of inflammatory biomarkers will be performed at visits V1 (-2 weeks), V4 and V5 (subsequent to six and 14 weeks of double-blind treatment respectively).

Blood withdrawal for the measurement of inflammatory biomarkers will be performed at approximately the same daytime (± 2 hours) but at 10:00 am at the latest at each respective visit.

Further details are described in the Central Laboratory Manual.

9.1.18.2 Measurement of Variables Describing Concentration of Inflammatory Biomarkers and metabolites in Blood Serum

The following inflammatory biomarkers will be measured in the collected blood serum:

1. Inflammatory mediators
(Human InflammationMAP[®] v.1, RBM)

Biomarker analyses will be performed by the Biomarker Laboratory. Exact procedures how to handle blood drawing, blood processing, storing and shipment are described in Section 9.4 and in the Central Laboratory Manual.

Database print-outs of the analysis data will be provided to the Investigator in a timely manner subsequent to data unblinding and no later than trial closeout and have to be filed in the Investigator's file together with the CRF data of the respective Subject.

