9.4 Biological Sample Retention and Destruction

PPD's global central laboratory will supply the investigational site with the necessary equipment for storage, labelling and shipment of the samples.

Paraffin embedded biopsies, prepared as described in the Biopsy Laboratory Manual (Appendix G), can be stored and shipped at room temperature. Labelling and shipment are described in the Central Laboratory Manual.

The Investigator is responsible for the proper storage of biological samples (i.e. blood samples for standard safety laboratory analyses, blood samples for inflammatory biomarker analyses, sputum materials) at approximately -20°C or below (preferably -80°C) until sample shipment.

All biological samples have to be clearly and fully labelled according to the Central Laboratory Manual. Biological samples should be sorted by Subject and visit such that all the samples from a given Subject are readily accessible. A sample inventory list of all biological samples must be included in each sample shipment. Packing and shipment of the biological samples must be in accordance with the current guidelines.

Further details for storage, labelling and shipment of (a) biopsy paraffin blocks, (b) standard safety laboratory blood samples, (c) sputum cell count samples, (d) sputum biomarker samples, and (e) biomarker blood samples are described in the Central Laboratory Manual.

PPD will analyse the standard safety laboratory parameters immediately, while the serum and sputum supernatant samples for inflammatory biomarkers analyses will be stored at -80°C at PPD's global central laboratory. On Sponsor's request the stored samples will be sent on dry ice from PPD's global central laboratory to the Biomarker Laboratory (RBM, Austin, Texas) for analysis. PPD will be advised of the shipping details. Frequency of shipments will be discussed between the Sponsor and PPD by case situation.

Aliquots of sputum and tissue samples of the biopsy material will be collected and stored for up to three years after the end of the trial for future analyses of biomarkers of scientific interest.

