1.3.4 Detailed Processing Procedure

1. Prepare Sputolysin (DTT) working solution by diluting the stock solution 1:10 with distilled water (e.g. 1 mL Sputolysin (DTT) stock + 9 mL distilled water) and mix thoroughly. Store the stock solution at room temperature. The working solution should be prepared fresh daily.
2. Determine the weight (volume) of the selected sputum plugs by weighing the tube and subtraction of the value of the empty tube.
3. Example: Sputum weight = 100 mg (100 μL)
4. Add 4 volumes of Sputolysin (DTT) working solution (Example: 400 μL)
5. Mix gently (by hand or slowly vortex) and incubate for 15 minutes at a bench rocker. This procedure should homogenize most sputum samples, but there are some samples in which the mucus is difficult to break down. After homogenization, add 4 volumes PBS to achieve a 9-fold final dilution of the sputum sample (Some small remaining undissolved plugs are frequently homogenized when the sample is gently mixed with PBS).

Example: Total volume after homogenization = 500 μL . 400 μL (4 times sputum volume of 100 μL) of PBS need to be added to the sample. Mix gently.

6. FILTRATION: Do not filter if total volume is <1 mL, proceed with unfiltered sample as described. Put a filter (50 μm nylon mesh), which has been pre-wetted with PBS, into the

funnel. Set the funnel into a pre-weighed conical tube and filter the cell solution through the nylon mesh. Record the total weight of the filtrate with the tube and subtract the weight of the empty tube to obtain the weight of the filtered cell solution. This way the loss of volume due to filtration can be estimated.

7. Centrifuge the homogenized and diluted sample at 600 g for 10 minutes at room temperature.
8. Take off the supernatant and disperse equally into labelled cryotubes.

Attention: Be careful to avoid aspiration of cells from the pellet. In case of aspiration, centrifuge sample once more.

The following information on the cryotube labels is mandatory:

- trial ID (i.e. RO-2455-402-RD)
- site/centre no.
- Subject ID
- visit no.
- visit date

Store them immediately until the end of the trial at -70°C to -80°C at each trial site.

Do not forget to document storage time!

Boxes containing the biomarker samples (including back-up samples) will be shipped on the sponsor's request.

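### Section 9.4 lets sites keep sputum supernatant at about -20°C, while Appendix H requires -70 to -80°C; serum has only the permissive limit, so storage of secondary-endpoint samples may differ by site

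*Protocol*

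**What the plan says.** Protocol Section 9.4 sets one storage rule for several sample types. Among those it names are "blood samples for inflammatory biomarker analyses, sputum materials". The investigator is to keep them "at approximately -20°C or below (preferably -80°C) until sample shipment". Once they reach the central laboratory the rule is stricter: "the serum and sputum supernatant samples for inflammatory biomarkers analyses will be stored at -80°C at PPD's global central laboratory".

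Appendix H (Sputum Laboratory Manual), Section 1.3.4, step 8, says of the supernatant cryotubes: "Store them immediately until the end of the trial at -70°C to -80°C at each trial site". Shortly afterwards it adds: "Boxes containing the biomarker samples (including back-up samples) will be shipped on the sponsor's request".

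Two cross-references bear on which text applies:

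- Sputum, Section 9.1.17.2: "Sputum supernatant samples will be handled and stored according to the instructions provided in the Sputum Laboratory Manual".
- Serum, Section 9.1.18.2: procedures for blood processing, "storing and shipment are described in Section 9.4 and in the Central Laboratory Manual". Section 9.4 likewise leaves further storage detail for sputum and blood biomarker samples to the Central Laboratory Manual.

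Sputum and serum mediators are secondary endpoints (Section 5.2.2), sampled at V1, V4 and V5. Section 13.1.3.3 analyses them by ANCOVA on change from baseline to the last available on-treatment value, with baseline, treatment and the stratification factor as covariates.

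**The concern.** Appendix H is part of the protocol, so a site has two instructions in one document for the same tube. They differ in temperature and, on their face, in how long the tube stays at site.

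Storage conditions are part of the measurement. If some sites hold samples at -20°C and others at -80°C, and if any analyte is less stable at the warmer temperature, measured concentrations would differ by site for reasons unrelated to treatment. The trial plans about 25 sites for 150 randomized subjects, an average of 150/25 = 6 per site. Randomization is stratified by LABA use only, and the ANCOVA has no site term, so differences between sites would go into the residual error. Because the V1 sample is collected about 16 weeks before the V5 sample, unequal time at site could also distort the change from V1 described within each arm. A sample that has deteriorated at site cannot be repaired in the analysis.

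**Working it through.** The plan states no figure to reproduce. The check compares the storage rules and then does the date arithmetic for the V1 to V5 interval.

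**Sputum supernatant**

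| | Section 9.4 | Appendix H, 1.3.4 |
|---|---|---|
| Temperature at site | about -20°C or colder, -80°C preferred | -70 to -80°C |
| Time at site | until shipment | until the end of the trial, but boxes go on request |
| After receipt centrally | -80°C | not stated |

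- A site at -70 to -80°C meets both temperature rules.
- A site at -20°C meets Section 9.4 and breaches Appendix H. This is a real conflict. The cross-reference in Section 9.1.17.2 shows which text was meant to apply, but it does not remove the looser sentence, which names sputum materials.
- On holding time the conflict is softer. Shipment on request in Appendix H can be read together with Section 9.4, but the instruction to hold until the end of the trial cannot be read with earlier shipment to the central laboratory.

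**Serum**

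- Appendix H does not cover serum, so nothing contradicts Section 9.4.
- Section 9.4 on its own permits anything from about -20°C down. Under Section 9.1.18.3 the metabolite panel uses the blood backup samples, so they come under the same sentence.
- The Central Laboratory Manual may set a tighter rule and a shipping interval. It is not available, so neither can be judged.

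**Interval between the V1 and V5 samples** (visit windows from Appendix A, in days)

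- V1 is day 28 after V0, window -2/+3: days 26 to 31.
- V2 is day 42 after V0, window -3/+5: days 39 to 47.
- V5 is day 98 after V2, window -3/+5: days 95 to 103.
- Nominal: 42 + 98 - 28 = 112 days (16 weeks).
- Shortest by windows alone: 39 + 95 - 31 = 103 days. Appendix F asks for at least 14 days from the V1 sputum sample to the V2 biopsy, which makes the shortest interval for sputum 14 + 95 = 109 days.
- Longest: 47 + 103 - 26 = 124 days, or 124 + 28 = 152 days if sputum induction at V5 is postponed four weeks for an exacerbation (Section 9.3.4).

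If all of a subject's samples leave the site together, the baseline sample has spent that much longer in the site freezer than the V5 sample. If sites ship after each visit, the extra time is spent at -80°C in the central laboratory and the difference at site temperature disappears. For supernatant, Appendix H points to the first case. For serum, the protocol gives no site shipping interval.

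**The case against.** The strongest reply is that an order of precedence already exists. Section 9.1.17.2 sends supernatant storage to Appendix H, and Section 9.4 is an umbrella sentence with an upper limit, so a site that follows Appendix H complies with everything. That is fair, and it means storage may differ by site, not that it does. It does not dispose of the point, because a site relying on Section 9.4 alone would have written support for -20°C.

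Several stronger readings are tempting, and the documents do not support them:

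- *Serum is governed only by the weaker rule, or the rules for serum contradict each other.* Sections 9.1.18.2 and 9.4 both also point to the Central Laboratory Manual, and Appendix H does not apply to serum.
- *Baseline supernatant sits at -20°C for 16 weeks longer than the V5 sample.* This joins the long hold in Appendix H to the temperature in Section 9.4. Appendix H pairs its long hold with -70 to -80°C, and Section 9.4 pairs -20°C only with storage until shipment. No single text prescribes a long hold at -20°C.
- *The apparent rise from baseline can be put as a percentage.* That needs a loss rate for each analyte at -20°C. The documents give none, and zero is not excluded.
- *The treatment comparison is biased.* Handling rules and visit times are the same in both arms.

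The consequence is also limited by the standing of the endpoints. Of the 46 analytes, six are of primary interest and the other 40 are exploratory, and metabolomics has its own analysis plan and report.

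**Conclusion.** The point holds in limited form. For sputum supernatant, Section 9.4 and Appendix H give incompatible site temperatures and loosely worded, partly incompatible holding times. For biomarker and metabolite serum, the protocol fixes a permissive limit that an unavailable manual may or may not tighten.

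The possible consequences are extra between-site noise in the secondary mediator endpoints and a distorted within-arm change from V1. Both depend on two things that the documents do not settle: whether any site uses -20°C, and whether any analyte is less stable there. The size is therefore unknown, and no percentage should be attached to it. The treatment contrast is not biased by design. The primary and key secondary endpoints, CD8+ and CD68+ counts, come from paraffin-embedded biopsies that Section 9.4 allows at room temperature, and are not touched.

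The wording should still be changed. It is a stated handling rule for secondary endpoints, and the protocol itself prefers -80°C and uses it centrally.

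**What to change.** In Section 9.4, take sputum supernatant and biomarker and metabolite serum out of the general sentence and require -70 to -80°C at site for them, matching Appendix H. In both Section 9.4 and Appendix H, state the same rule for how long samples stay at site and when they are shipped to the central laboratory. Check that the Central Laboratory Manual agrees.

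The cost is protocol wording. Appendix H already requires -70 to -80°C storage at every site, so no new type of freezer is implied; the serum tubes would share that space. Any sensitivity analysis for samples held at a warmer temperature can be left to the statistical analysis plan.

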10.0 ADVERSE EVENTS

10.1 Definitions

10.1.1 AEs

An AE is defined as any untoward medical occurrence in a clinical investigation subject administered a drug; it does not necessarily have to have a causal relationship with this treatment.

An AE can therefore be any unfavorable and unintended sign (eg, a clinically significant abnormal laboratory finding), symptom, or disease temporally associated with the use of a drug whether or not it is considered related to the drug.

10.1.2 Additional Points to Consider for AEs

An untoward finding generally may:

- Indicate a new diagnosis or unexpected worsening of a pre-existing condition. (Intermittent events for pre existing conditions underlying disease should not be considered AEs.)
- Necessitate therapeutic intervention.
- Require an invasive diagnostic procedure.
- Require discontinuation or a change in dose of study medication or a concomitant medication.
- Be considered unfavorable by the investigator for any reason.
- AEs caused by a study procedure (eg, a bruise after blood draw) should be recorded as a AE.

Diagnoses vs signs and symptoms:

- Each event should be recorded to represent a single diagnosis. Accompanying signs (including abnormal laboratory values or ECG findings) or symptoms should NOT be recorded as additional AEs. If a diagnosis is unknown, sign(s) or symptom(s) should be recorded appropriately as an AE(s).

Laboratory values and ECG findings:

- Changes in laboratory values or ECG parameters are only considered to be AEs if they are judged to be clinically significant (ie, if some action or intervention is required or if the investigator judges the change to be beyond the range of normal physiologic fluctuation). A laboratory re-test and/or continued monitoring of an abnormal value are not considered an intervention. In addition, repeated or additional noninvasive testing for verification, evaluation or monitoring of an abnormality is not considered an intervention.
- If abnormal laboratory values or ECG findings are the result of pathology for which there is an overall diagnosis (eg, increased creatinine in renal failure), the diagnosis only should be reported appropriately as an AE.

Pre-existing conditions:

- Pre-existing conditions (present at the time of signing of informed consent) are considered concurrent medical conditions and should NOT be recorded as AEs. Baseline evaluations (eg, laboratory tests, ECG, X-rays etc.) should NOT be recorded as AEs unless related to study procedures. However, if the subject experiences a worsening or complication of such a concurrent condition, the worsening or complication should be recorded appropriately as an AE (worsening or complication occurs before start of study medication) or an AE (worsening or complication occurs after start of study medication). Investigators should ensure that the event term recorded captures the change in the condition (eg, “worsening of...”).
- If a subject has a pre-existing episodic condition (eg, asthma, epilepsy) any occurrence of an episode should only be captured as an AE if the episodes become more frequent, serious or severe in nature, that is, investigators should ensure that the AE term recorded captures the change in the condition from Baseline (eg “worsening of...”).
- If a subject has a degenerative concurrent condition (eg, cataracts, rheumatoid arthritis), worsening of the condition should only be captured as a AE if occurring to a greater extent to that which would be expected. Again, investigators should ensure that the AE term recorded captures the change in the condition (eg, “worsening of...”).

Worsening of AEs:

- If the subject experiences a worsening or complication of an AE after starting administration of the study medication, the worsening or complication should be recorded appropriately as an AE. Investigators should ensure that the AE term recorded captures the change in the condition (eg, “worsening of...”).
- If the subject experiences a worsening or complication of an AE after any change in study medication, the worsening or complication should be recorded as a new AE. Investigators should ensure that the AE term recorded captures the change in the condition (eg, “worsening of...”).

Changes in severity of AEs:

- If the subject experiences changes in severity of an AE, the event should be captured once with the maximum severity recorded.

Preplanned surgeries or procedures:

- Preplanned procedures (surgeries or therapies) that were scheduled prior to signing of informed consent are not considered AEs. However, if a preplanned procedure is performed early (eg, as an emergency) due to a worsening of the pre-existing condition, the worsening of the condition should be captured appropriately as an AE. Complications resulting from any planned surgery should be reported as AEs.

Elective surgeries or procedures:

- Elective procedures performed where there is no change in the subject's medical condition should not be recorded as AEs, but should be documented in the subject's source documents. Complications resulting from an elective surgery should be reported as AEs.

Insufficient clinical response (lack of efficacy):

- Insufficient clinical response, efficacy, or pharmacologic action, should NOT be recorded as an AE. The investigator must make the distinction between exacerbation of pre-existing illness and lack of therapeutic efficacy.

Overdose:

- Cases of overdose with any medication without manifested side effects are NOT considered AEs.

10.1.3 SAEs

An SAE is defined as any untoward medical occurrence that at any dose:

1. Results in DEATH.
2. Is LIFE THREATENING.
 - The term "life threatening" refers to an event in which the subject was at risk of death at the time of the event; it does not refer to an event that hypothetically might have caused death if it were more severe.
3. Requires inpatient HOSPITALIZATION or prolongation of existing hospitalization.
4. Results in persistent or significant DISABILITY/INCAPACITY.
5. Leads to a CONGENITAL ANOMALY/BIRTH DEFECT.
6. Is an IMPORTANT MEDICAL EVENT that satisfies any of the following:
 - May require intervention to prevent items 1 through 5 above.
 - May expose the subject to danger, even though the event is not immediately life threatening or fatal or does not result in hospitalization.
 - Includes any event or synonym described in the Takeda Medically Significant AE List (Table 10.a).

Table 10.a Takeda Medically Significant AE List

Term	
Acute respiratory failure/acute respiratory distress syndrome	Hepatic necrosis
Torsade de pointes / ventricular fibrillation / ventricular tachycardia	Acute liver failure Anaphylactic shock
Malignant hypertension	Acute renal failure
Convulsive seizure	Pulmonary hypertension
Agranulocytosis	Pulmonary fibrosis
Aplastic anemia	Confirmed or suspected endotoxin shock
Toxic epidermal necrolysis/Stevens-Johnson syndrome	Confirmed or suspected transmission of infectious agent by a medicinal product Neuroleptic malignant syndrome / malignant hyperthermia Spontaneous abortion / stillbirth and fetal death

AEs that fulfill 1 or more of the serious criteria above are also to be considered SAEs and should be reported and followed up in the same manner (see Sections 10.2.2 and 10.3).

10.1.4 Severity of AEs

The different categories of intensity (severity) are characterized as follows:

- Mild: Transient symptoms, no interference with the Subject's daily activities.
Moderate: Marked symptoms, moderate interference with the Subject's daily activities
Severe: Considerable interference with the Subject's daily activities..

